### 11.1.3 Concomitant Medications / Interactions

For management of concomitant therapies, please refer to the latest mirtazapine Summary of Product Characteristics (produced by Medreich Plc; PL 21880/0053).

Use of MAO inhibitors, linezolid, other antidepressant medication, and St John's wort are prohibited for the participant for the duration of the trial. Furthermore, MAO inhibitors must not be used until there has been a 14 day washout period from the last dose of IMP.

Caution is advised (particularly in relation to dose escalation) when used with inhibitors or inducers of CYP3A4, benzodiazepines, alcohol and warfarin.

## 11.1.4 Most frequent anticipated toxicities

The most frequent anticipated toxicities of mirtazapine are as follows:

- Increased appetite •
- Weight gain
- Somnolence
- Sedation •
- Headache •
- Dry mouth •
- Lethargy •
- Dizziness •
- Tremor •
- Nausea •
- Diarrhoea
- Vomiting

- Exanthema
- Arthralgia
- Myalgia
- Back pain
- Orthostatic hypotension
- Oedema peripheral
- Fatigue
- Abnormal dreams
- Confusion
- Anxiety
- Insomnia

#### 11.2 **Emergency Unblinding**

Whilst the safety of participants in the trial must always take priority, maintenance of blinding is crucial to the integrity of the trial. Investigators should only break the blind when information about the participant's trial treatment is clearly necessary for the appropriate medical management of the participant and where stopping the blinded medication is not sufficient.

Unblinding may be requested on the grounds of safety by the Chief Investigator (CI), local PI or treating physician. It is anticipated that requests for unblinding will most likely originate from a participant, carer (or friend / family member) or personal physician (e.g. GP) at the time of an adverse event or planned change in non-trial related drug therapy. Requests for unblinding will first be handled by the local PI or delegate who will explore the reason for the request and evaluate the importance of knowledge of treatment assignment for participant safety. In the

event of a Serious Adverse Event (SAE), all participants should be treated as though they are receiving the active medication.

Should an alternative to unblinding not be identified, and if unblinding is required to optimise medical management of the participant, investigators should follow the emergency unblinding process.

Emergency unblinding is provided by the CTRU during Office Hours and the participating site pharmacy at all other times, thereby covering each 24-hour period. It is encouraged that requests for Emergency Unblinding should be made directly with CTRU wherever possible.

The following information will be needed to perform an emergency unblinding:

- Participant details, including trial ID number, initials and date of birth
- Name of trial research site and site code
- Name of person making the request for a code-break
- Reason for requesting a code-break
- Confirmation of whether the PI authorised the request

#### **11.2.1 Emergency Unblinding during Office Hours**

The emergency unblinding process will be undertaken by telephoning the CTRU during Office Hours, 9.00 to 17.00 Monday to Friday. Exceptions: public / bank holidays, the period between Christmas Eve and New Year, Thursday afternoon before Good Friday and all Tuesdays following a bank holiday except for Mayday and New Year's Day.

# **Direct line for CTRU emergency unblinding: [name]**

Following the emergency unblinding of a participant, CTRU will send a notification to the requester, the local PI and the Sponsor. The details of the emergency unblinding should be recorded on the BETTER-B Unblinding Log provided by CTRU.

#### **11.2.2 Emergency Unblinding outside of Office Hours**

Outside of Office Hours, or where the Investigator or treating physician is unable to contact CTRU, emergency unblinding must be performed by the local pharmacy department. The responsible pharmacist on duty will complete the Unblind Request CRF, retrieve the code-

break information (Code-Break Envelopes for unblindings will be provided to pharmacy at the time of IMP delivery and each envelope will be linked to a specific container of capsules using a unique kit-code) and reveal the treatment allocation to the person requesting the unblind. The pharmacist must send the completed Unblind Request CRF to the CTRU within 24 hours of the unblinding request (please see section 21 for details of acceptable methods of transfer).

All Code-Break Envelopes will be returned to CTRU by the site pharmacy department at the end of trial. Code-Break Envelopes must not be opened for participants when they have completed trial therapy.

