# 10.2 Supply, Distribution and Storage

Trial IMPs (mirtazapine and placebo) will be provided to sites free of charge for use in this clinical trial. Blinded supplies will be sent to trial sites from Central Pharmacy (see above) in pre-labelled containers which will be identifiable by a kit-code printed on the label. In addition to the trial IMP containers, sites will receive sealed Code-Break Envelopes to allow emergency unblindings where necessary. Each envelope will be linked to a specific container of trial IMP capsules using the unique kit-code system. See section 11.2 below for further details on emergency unblinding.

Once received from the trial Central Pharmacy, all trial IMP stock and Code-Break Envelopes must be documented as received in accordance with the BETTER-B Pharmacy and IMP SSOP provided within the BETTER-B Pharmacy Site File.

All trial IMP containers must be stored in a secure ring-fenced location within the site pharmacy. There are no special storage requirements in terms of temperature management.

The supply of trial IMPs (mirtazapine and placebo) must not be used for any purpose other than that outlined in this protocol and should be clearly ring-fenced from standard hospital stock.

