# 10.3 Dispensing

In order to maintain the blinding of the trial the site pharmacist will not be told the participant's treatment allocation. Blinded containers of capsules, identifiable only by a unique kit-code are received at site pharmacies from the Central Pharmacy and will be stored in a ring-fenced section of the site pharmacy until dispensing. To ensure that the correct treatment is dispensed to the participant the relevant site pharmacist will be told which container to dispense to each participant using this kit-code numbering system.

The relevant site pharmacist will be notified by the CTRU of all participants randomised at that site; each Confirmation of Randomisation notification will detail the participant trial ID number, date of birth and initials and also the kit-code assigned to that participant which will identify which container of capsules should be given to the participant. The member of the local research team randomising the participant will also have been told which kit-code should be dispensed to the participant whilst making the randomisation telephone call, and will also receive a Confirmation of Randomisation Fax detailing the kit-code.

The participant's trial identifier must be added to the label of each trial IMP container by the pharmacist (or authorised delegate) at the time of dispensing, and the Code-Break Envelope assigned to that kit-code annotated with the participant details and then securely stored in pharmacy.

Dispensing must only be performed by an authorised member of site staff as delegated on the trial Pharmacy Authorised Personnel Log. Once randomised, at baseline the participant will receive one trial IMP container, containing 42 capsules, of either mirtazapine or placebo, identifiable only by the unique kit-code on the outer container label. All dispensed trial IMP must be recorded on the trial Accountability and Dispensing Log in accordance with the BETTER-B Pharmacy and IMP SSOP.

Each container of trial IMP capsules, identifiable only by the unique kit-code, will have a corresponding Code-Break Envelope. Each time a container of capsules is dispensed, the participant identifiers must be added to the trial IMP container label and also to the corresponding Code-Break Envelope. This Code-Break Envelope will then be held securely within the site pharmacy (see section 11.2 for access required in the event of unblinding).

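### Section 11.2.2 bars opening code-break envelopes once trial therapy is completed, with no emergency exception, although section 11.2 offers round-the-clock emergency unblinding

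*Protocol*

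**What the plan says.** Protocol section 11.2 opens with a priority: "Whilst the safety of participants in the trial must always take priority". It allows a code-break only when the allocation is clearly needed to manage the participant medically and "where stopping the blinded medication is not sufficient". It also says that, in the event of a serious adverse event, "all participants should be treated as though they are receiving the active medication". On availability it states: "Emergency unblinding is provided by the CTRU during Office Hours and the participating site pharmacy at all other times, thereby covering each 24-hour period". Nothing there limits this cover to participants still taking trial drug.

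Section 11.2.1 describes the CTRU telephone route, 9.00 to 17.00 Monday to Friday with listed holiday closures. It places no condition on treatment status.

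Section 11.2.2 covers all other times, and any occasion when CTRU cannot be reached. Then "emergency unblinding must be performed by the local pharmacy department", with the duty pharmacist obtaining the allocation from the envelope linked to the kit-code. Section 10.2 gives the purpose of the envelopes: "sites will receive sealed Code-Break Envelopes to allow emergency unblindings where necessary". Section 10.3 defers to 11.2 on access: "see section 11.2 for access required in the event of unblinding".

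The last sentence of 11.2.2, directly after the instruction to return envelopes at the end of the trial, reads: "Code-Break Envelopes must not be opened for participants when they have completed trial therapy".

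**The concern.** The duty pharmacist has three statements to reconcile: a mandatory duty to perform the emergency unblinding, a general priority for safety, and a flat prohibition on using the only tool supplied. For a participant who has completed treatment, these cannot all be followed. Whether a justified code-break is allowed then depends on the hour of the request and not on medical need.

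What is at stake is delay to a justified code-break until CTRU can be reached. It is a matter of participant safety and internal consistency. No sample size, endpoint or analysis depends on it.

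**Working it through.** The protocol states no figure to reproduce. The check sets the provisions side by side and then works out how much of the week they affect.

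**1. The routes, by treatment status**

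| Situation | On treatment | Completed treatment |
|---|---|---|
| Office hours, CTRU reachable (11.2.1) | CTRU may unblind | CTRU may unblind; no bar stated |
| Out of hours, or CTRU not reachable (11.2.2) | Pharmacy opens envelope | Pharmacy must unblind, but envelope must not be opened |

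The bottom right cell is the contradiction. No other section gives an exception. No second out-of-hours route is described: under section 10.1 the back-up kit-code lists are kept by the CTRU trial statistician, and no section gives the pharmacy a copy.

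**2. Who is caught**

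Footnote xiv in section 11.1.2 uses *completed* for 28 days of treatment. Section 12.7 uses *discontinues* for stopping before that. On ordinary usage the bar therefore covers those who finish the 28 days and not those who stop early.

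**3. Whether the period after treatment matters in this protocol**

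It does. Adverse events are collected until 7 days after the last dose (section 13.3.1). Serious and unexpected reactions remain reportable until 90 days after the end of the trial (section 13.3.2). The envelopes are returned only at the end of the trial (sections 10.4 and 11.2.2), so for most completers the envelope is still at the site but may not be used.

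**4. How much of the week is affected**

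Inputs: CTRU hours 09:00 to 17:00, five days a week (section 11.2.1); 7 × 24 = 168 hours in a week.

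- CTRU cover: 5 × 8 = 40 h; 40/168 = 23.8%.
- Envelope only: 168 − 40 = 128 h; 128/168 = 76.2%.
- Holiday closures only reduce the 40, so 40 is a maximum and 128 a minimum.

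**5. Length of the possible delay under a strict reading**

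- Weeknight, 17:00 to 09:00: 7 + 9 = 16 h.
- Ordinary weekend, Friday 17:00 to Monday 09:00: 7 + 24 + 24 + 9 = 64 h.
- Check: 4 weeknights × 16 + 64 = 128 h, as in step 4.

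These are the longest waits in a week without a holiday, for a request made just after CTRU closes. Holiday closures lengthen them.

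**The case against.** The strongest reply is that the sentence is housekeeping. It sits beside the rule on returning envelopes, while the emergency procedure is in the paragraph before it, so its natural purpose is to stop sites opening envelopes out of curiosity when a participant finishes. That is probably the intent. But the sentence does not contain the word *routinely*, and it closes the section that governs emergency opening.

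A second reply is that the safety priority in section 11.2 tells the pharmacist which statement prevails. It does help. It is, however, a general principle and not an exception to a specific prohibition, and a pharmacist on duty should not have to infer one.

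A third is that the test about stopping the medication presupposes a participant still taking it, so the 24-hour cover was never meant for completers. That reading is possible, but section 11.2 does not say so, and 11.2.1 leaves CTRU free to unblind completers.

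Several points on the other side stand and limit the weight of the finding:

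- Clinical need will be rare. The drug has stopped, and a participant with a serious adverse event is managed as if on mirtazapine.
- The 14-day gap before monoamine oxidase inhibitors (section 11.1.3) creates no need for a code-break. It runs from the last dose of trial product, and section 10 classes placebo as trial product, so it binds both arms.
- The 76% would be the same for any trial with a weekday office and says nothing about how often completers need unblinding.
- Section 10 refers to a Pharmacy and IMP operating procedure that is not shown and may already allow emergency opening. If it does, it conflicts with the protocol sentence, which would still need correcting.
- The blind still has value after completion, because toxicity is collected at the call 7 days after treatment ends.

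**Conclusion.** The point holds and is minor. As written, section 11.2.2 removes the only described out-of-hours route for participants who have completed treatment, while section 11.2 offers cover at all hours on the basis of medical need. The gap spans at least 128 of 168 hours a week (76%), and a strict reading could delay a code-break by up to 64 hours over an ordinary weekend.

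The protocol gives no rate of emergencies after completion. The expectation of few or none is a judgement based on about 60 participants, a drug already stopped, and the strict test in section 11.2.

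The conclusion rests on reading the sentence literally and on the protocol alone. Confidence is medium, because the intended meaning was probably narrower and the pharmacy procedure is not available.

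**What to change.** Replace the last sentence of section 11.2.2 with wording such as:

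> *Code-break envelopes must not be opened routinely after a participant has completed or stopped trial therapy; emergency opening under the section 11.2 test remains permitted.*

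Adding *or stopped* is deliberate: it extends the bar on routine opening to participants who discontinue early, whom the present sentence appears to miss. Check that the Pharmacy and IMP operating procedure says the same.

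The cost is one sentence and one document check. The only downside is a rare extra code-break. It would usually fall after the day 28 outcomes are collected, though possibly before the toxicity call 7 days after treatment ends, in which case that participant's last toxicity assessment might not be blinded. Sample size, endpoints and analysis are unchanged.

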## 11.2.3 Treatment of Participants following Emergency Unblinding

Following an emergency unblinding the participant should be treated according to the treating clinician's assessment.

# 11.3 Withdrawal of Treatment

In line with usual clinical care, cessation or alteration of regimens at any time will be at the discretion of attending clinicians or the participants themselves. All participants withdrawn from treatment or prescribed alternative treatment will still attend for follow-up assessments unless unwilling to do so and CRFs will continue to be completed.

The PI, or delegate should make every effort to ensure that the specific wishes of any participant who wishes to withdraw consent for further involvement in the trial are defined and documented using the Withdrawal CRF in order that the correct processes are followed by the CTRU and site following the withdrawal of consent.

It should be made clear to any participant specifically withdrawing consent for further data collection that data pertaining to safety will continue to be collected for regulatory reporting purposes and will be included in any safety analysis. In addition it is suggested that the participant is made aware of the fact that if any significant new information becomes available in regard to the treatment they have received in the trial it may be necessary to contact them in the future.

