A number of participant-reported questionnaires will also be completed. These may be completed by the participants themselves, or, if preferred, by a member of the research team on behalf of the participant. Where this is the case, separate booklets are provided for staff to complete, along with a number of laminated "prompt sheets" to be given to the participant to facilitate this process.

- Modified Medical Research Council (mMRC) dyspnoea scale
- Chronic Respiratory Questionnaire (CRQ)
- Integrated Palliative care Outcome Scale (IPOS)
- Hospital Anxiety and Depression Scale (HADS)
- EQ-5D-5L
- Generalized Self-Efficacy Scale (GSES)
- Client Services Receipt Inventory (CSRI)
- Blinding Assessment

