# 12.6 Follow-up Assessment and Data Collection

Participants will be followed-up 7 daysxxxii after the end of trial treatment. The research team will contact the participant by phone to perform the following assessments:

• Toxicity assessment: collection of any adverse events or reactions which may have occurred since the participant stopped trial treatment

<sup>xxxii Where this phone-call cannot take place exactly 7 days after the end of trial treatment, it must not be earlier than 7 days after completing treatment, and should be no more than 1 working day later.

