#### 13.3.1 Reporting of Adverse Events (AEs) and Adverse Reactions (ARs)

All AEs occurring from randomisation up to 7 days after the last dose of trial treatment and all ARs occurring from the first trial treatment dose up to 7 days after the last dose of trial treatment must be recorded on the appropriate Trial Treatment Assessment CRF or Follow-up Assessment CRF, which will be posted to CTRU within 2 weeks of the assessment. These are not subject to expedited reporting to CTRU.

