### 18.2 Analysis populations

The primary endpoint analysis will be based on the population of participants randomised within the 12-month recruitment period.

Endpoints which relate to data collected prior to randomisation will be analysed using all patients approached for entry to the study.

Analyses of safety data will be carried out on the safety population, defined as those participants receiving at least one dose of trial treatment, and will summarise participants according to the treatment actually received.

The remaining analysis will be carried out on the intention-to-treat (ITT) population defined as all participants randomised to the trial, regardless of adherence to the protocol, withdrawal of consent or losses to follow-up. Participants will be included within the treatment arm to which they were randomised.

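### The protocol does not make clear whether day-28 NRS and blinding are still collected after early stopping of treatment, and the post-treatment call does not ask about the days before the stop

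*Protocol*

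**What the plan says.** **Early stopping.** Section 11.3 of the protocol keeps participants who leave treatment in the trial: "All participants withdrawn from treatment or prescribed alternative treatment will still attend for follow-up assessments unless unwilling to do so". The sentence ends "unless unwilling to do so and CRFs will continue to be completed". It does not list the assessments meant.

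**Follow-up assessment.** Section 12.6 describes one contact, 7 days "after the end of trial treatment. The research team will contact the participant by phone to perform the following assessments". The only item listed is: "Toxicity assessment: collection of any adverse events or reactions which may have occurred since the participant stopped trial treatment". Table 1 agrees, apart from a compliance check for anyone whose 28 days were incomplete at the Day 28 visit. The Trial Summary also separates the weekly assessments during treatment from a follow-up assessment by phone 7 days after the last dose.

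**Weekly assessments.** Sections 12.5.1 to 12.5.4 place the day 7, 14, 21 and 28 contacts at those days of trial treatment. All four include NRS. The "Blinding Assessment" is listed at day 28 only.

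**Adverse events.** Section 13.3.1 requires every adverse event from randomisation to 7 days after the last dose to be captured; these "must be recorded on the appropriate Trial Treatment Assessment CRF or Follow-up Assessment CRF".

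**Analysis.** In section 18.2 the intention-to-treat (ITT) population is "defined as all participants randomised to the trial, regardless of adherence to the protocol". Section 16.2 makes worst NRS at day 28 the key activity endpoint. It also lists maintained blinding, remaining on study for 28 days and missing data as feasibility endpoints.

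**The concern.** Among other things, this trial is meant to show how many participants are lost, how complete the day-28 outcome is and whether the blind holds. Early stoppers bear on all three, and the protocol is least clear about them.

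If a site takes follow-up assessment in the sense of section 12.6, a participant who stops treatment gets one toxicity call and no further NRS or blinding question. Stopping treatment and missing the outcome would then coincide, and the day-28 NRS would come mainly from people still on treatment. The blinding data would omit people who stopped because of side effects, whose guesses may well differ from the rest. Another site could take the same sentence to mean that all remaining visits continue, so practice could differ between the three sites.

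The look-back of the call is a separate matter. It arises for any early stopper who has no further weekly assessment, whichever reading is taken.

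**Working it through.** **1. The two senses of follow-up.**

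| Points to the single call | Points to the remaining visits |
|---|---|
| Trial Summary and section 12.6 use the term for the post-treatment call | Section 11.3 says participants attend, uses the plural, and keeps CRFs going |
| Section 7 describes follow-up as the 7 days after treatment, for safety and toxicity | Section 9.3.2 uses follow-up data in a general sense, to protect the ITT analysis |
| Section 13.3.1 names separate CRFs for treatment assessments and follow-up | Section 21 separates withdrawal from treatment from withdrawal from data collection |
| Sections 12.5.1 to 12.5.4 count days of trial treatment | Table 1 labels its columns by day alone |
| Section 13.4 speaks of attending for follow-up, although the only scheduled follow-up is a call | Section 18.5.1 reports remaining on study separately from stopping treatment |

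Neither column settles it. No section says that the day 7 to 28 assessments continue on the original calendar after a stop.

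**2. A participant who stops on day 10, last contacted on day 7.**

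- *Narrow reading:* a call on day 17 (10 + 7) covering events since day 10, then nothing. There is no day-28 NRS and no blinding question, and days 8 to 10 are not prompted.
- *Broad reading:* the day 14 visit asks about everything since the day 7 call, so days 8 to 10 are covered. NRS and blinding are obtained at day 28.
- *Broad reading, but the participant declines visits and takes the call:* same gaps as the narrow reading.

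**3. The look-back chain.** The day 7 prompt starts at baseline, day 14 at the day 7 call, day 21 at the day 14 visit and day 28 at the day 21 call. Only section 12.6 starts at the stop date. With weekly contacts kept until the stop, the unprompted interval is at most about 7 days per early stopper.

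**4. Size.** Inputs from section 17: 60 participants, 30 per arm, 20% expected attrition, about 90 per arm and about 230 in total for the future trial.

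- The plan's own use of the 20%: 90 / (1 − 0.20) = 112.5, rounded up to 113 per arm; 2 × 113 = 226. This agrees with the stated 230 or so.
- Without a day-28 NRS, if all attrition is early stopping and the narrow reading is followed: 60 × 0.20 = 12, leaving 48, or 24 per arm if evenly split. At 10%: 60 × 0.10 = 6. At 30%: 60 × 0.30 = 18.
- Precision of the day-28 SD in one arm: the 95% limits are the estimate times √[(n − 1)/χ²(0.975; n − 1)] and √[(n − 1)/χ²(0.025; n − 1)]. For n = 30 the multipliers are 0.80 and 1.34; for n = 24 they are 0.78 and 1.40. The loss of precision is modest. The larger worry is that those missing are not a random subset.
- The number of early stoppers stays known from the End of Trial Treatment CRF (section 12.7). At 12/60 = 20%, the exact 95% interval is 11% to 32%.

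**The case against.** The strongest reply is that the ordinary meaning of section 11.3 is the broad one. Nobody attends a phone call, the plural suits several visits, CRFs continue, and ITT includes everyone randomised. This has force, and it rules out saying that the protocol ends assessment at the stop. It does not remove the ambiguity: section 13.4 itself speaks of attending for follow-up, the Follow-up Assessment form is itself a CRF, and ITT membership decides who is analysed without scheduling any measurement.

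A reader might also infer that the adverse events leading to a stop are lost. The documents do not support that. Sections 13.3 and 13.3.1 require all events from randomisation to be recorded, section 13.4 makes the investigator responsible for checking, and serious events are expedited under section 13.3.2. Any early stop triggers its own CRF, and section 18.5.1 reports the reasons. What stands is narrower: the call prompt omits an interval that the recording duty covers. The protocol does not say that the End of Trial Treatment CRF records the CTCAE grade, which section 18.5.3 needs for its summary of maximum grade.

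It is fair to add that a single blinding assessment at day 28 is a legitimate choice and that a guess at stopping measures something different. Actual unblinding is reported separately. The 20% in section 17 is general attrition; in advanced disease it will include deaths and withdrawals that no rewording recovers. Activity and toxicity outcomes do not decide whether the large trial proceeds.

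**Conclusion.** The point holds as an ambiguity and a mismatch in data collection.

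- Section 11.3 can be read as ending NRS and blinding assessment when treatment stops. The stronger inference, that stopping automatically loses the day-28 outcome or overstates attrition, is a risk of one plausible reading and not what the protocol fixes.
- The section 12.6 look-back is a stated rule that leaves non-serious events between the last completed contact and the stop unprompted at that call, contrary to the intent of section 13.3.1. Those events are unprompted, not lost.
- Anyone who does not reach the day 28 visit is never asked the blinding question, on either reading.

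The upper figure is 12 of 60 without a day-28 NRS (6 at 10%, 18 at 30%). It assumes that all attrition is early stopping and that sites follow the narrow reading; the recoverable part is smaller by an amount the documents do not give. The count of early stoppers, the primary recruitment endpoint and the stated sample sizes are unaffected. The change is worth making because these are data that the trial is run to collect.

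**What to change.** 1. In section 11.3, with a matching line in section 12.5, state that after early stopping the remaining day 7, 14, 21 and 28 assessments, including NRS and blinding, continue on the calendar from first dose unless the participant declines, in addition to the post-treatment call.
2. In section 12.6, start the look-back at the last completed assessment, consistent with section 13.3.1.
3. For participants who will not attend day 28, ask the blinding question at early stopping or at the post-treatment call, and report those answers separately from the day-28 guesses.

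The cost is protocol wording, one CRF item and a few more contacts with early stoppers, some of whom will decline. These changes concern data collection only and leave treatment decisions as they are.
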